### 2.2 Study design

At the time of oocyte aspiration, patients will be randomised in two groups:

- Control group: At the time of their fresh embryo transfer couples will receive a document with a photo of their transferred embryo(s) and the number of cryopreserved embryos.
- Intervention group: At the time of their fresh embryo transfer couples will receive a document with the following feedback (Appendix 5): a photo of their transferred embryo, the number of cryopreserved embryos, the quality rating of the transferred embryo's (i.e. ★, ★★, ★★★, ★★★★, appendix 6), and couple's personalized IVF-prognosis (i.e. their chance on a live birth from the current IVF-cycle, including the transfer of fresh and if available cryopreserved embryos), calculated by entering eight background characteristics and five IVF-laboratory results into a prognostic model (Appendix 7).

Firstly, we wish to analyse whether personalized information on IVF-prognosis on the day of their fresh embryo transfer results in more realistic expected IVF-live birth rates.

Secondly, we wish to evaluate whether sharing these IVF-prognosis with patients at the time of embryo transfer is associated with the anxiety experienced by patients.

Thirdly, we wish to explore whether these IVF-live birth rates expected by patients are associated with the infertility specific distress experienced by patients at the time of a negative pregnancy test.

Fourthly, we wish to follow-up whether these IVF-live birth rates expected by patients are associated with clinical and compliance outcomes.

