### 3.1.2 Sample size calculation

Hypothesizing that the intervention can lower the proportion of women expecting their live birth rate to be double their calculated IVF-prognosis from 50% to 25% dictates a sample size of 64 women per group (two-sided test; power 80%;  $\alpha=0.05$ ; G\*Power). To account for a 25% chance of study drop-out due to no embryos for transfer, not filling-out the questionnaires or loss of follow-up, 80 women will be recruited per group.

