### 4.6 Association between IVF-live birth rates expected by patients and infertility specific distress

Whether the intervention and control group, differ in infertility specific distress on the day of their embryo transfer will be analysed by comparing both group's IDS-score with an independent sample t-test. A p-value  $\leq 0.05$  will be considered statistically significant and the mean difference in infertility specific distress between both groups and its 95%

confidence interval will be reported. In addition, a linear (mixed or non-mixed) model will explore in the entire sample whether IVF-live birth rates expected by patients are associated with their infertility specific distress. We will examine whether gender significantly ( $p \leq 0.05$ ) affects the association between the IVF-live birth rate expected by patients and their infertility specific distress. If it does, we will rely on linear (non-mixed) models per gender. If it does not, we will rely on linear mixed models while including 'couple number' as a random factor to take account of clustering within couples, as partners cannot be considered independent cases.

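### Section 4.6 lets a significance test on gender choose between separate and pooled models; slopes then read as gender-specific can have the wrong error rates when men and women differ

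*Combined protocol and SAP*

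**What the plan says.** Section 2.2 gives as the third aim to explore "whether these IVF-live birth rates expected by patients are associated with the infertility specific distress experienced by patients" when a pregnancy test is negative. Section 4.6 carries this out: "a linear (mixed or non-mixed) model will explore in the entire sample", so both arms and both partners are analysed together.

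The choice of model is then made from the data:

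- The test: "We will examine whether gender significantly ( $p \leq 0.05$ ) affects the association" between expected rate and distress.
- The two branches that follow from it: "If it does, we will rely on linear (non-mixed) models per gender. If it does not, we will rely on linear mixed models". The mixed models carry couple number as a random factor, on the ground that "partners cannot be considered independent cases".

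The section does not adjust for the choice, does not say that the results of both branches will be shown, and does not say how a pooled slope should be read for each gender. Section 4.1 applies p ≤ 0.05 throughout. The 95% confidence interval promised in section 4.6 is for the between-arm difference in IDS score; none is stated for this association model.

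**The concern.** A two-stage rule of this kind treats absence of a significant interaction as evidence that the slopes are the same. The trial was sized for a binary outcome in women, and no power is given for a gender interaction. If the slopes differ and the test misses it, one common slope stands for both partners. An association carried by the women can then be read as applying to the men. If the test is significant, the separate slopes come from samples selected for a large difference. In both cases the final p-value, and any interval that accompanies it, is calculated as if the model had been fixed in advance.

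At stake is the answer to the third aim, in particular any statement about men and women separately.

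**Working it through.** **1. The plan's own figure.** Section 4.6 states no sample size or error rate. The only calculation is in section 3.1.2: "double their calculated IVF-prognosis from 50% to 25% dictates a sample size of 64 women per group". For 50% versus 25%, two-sided α = 0.05, the exact power of Fisher's test is 79.4% at 63 per group and 80.2% at 64, so 64 is reproduced. This gives 2 × 64 = 128 couples if exactly that many are analysable, and 2 × 80 = 160 if all recruits are. The number with an IDS score could be lower, since the third aim concerns a negative pregnancy test.

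**2. Assumptions.** Expectations and residuals are standardised, and partners are correlated in both. The rule was simulated as written: test the interaction at 0.05 in a random-couple model; if significant, fit ordinary least squares per gender; otherwise fit one pooled slope. A gender main effect was kept, which favours the plan. The comparator is one interaction model reported whatever its p-value. Residual variances were equal in men and women, except in step 5.

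**3. Results.** Correlations 0.5 (expectation) and 0.3 (residual), except the first row (0.3 and 0.3); male slope 0; 4,000 trials per row:

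| Couples | Slope, women | Splits | Coverage W / M | Male slope significant | One model: coverage W / M | One model: male slope significant |
|---|---|---|---|---|---|---|
| 128 | 0 | 5.2% | 93.2 / 93.2% | 6.8% | 94.2 / 94.6% | 5.4% |
| 128 | 0.1 | 14.3% | 88.0 / 88.2% | 11.8% | 95.7 / 94.8% | 5.2% |
| 128 | 0.2 | 43.7% | 79.1 / 79.2% | 20.7% | 94.5 / 94.9% | 5.1% |
| 128 | 0.3 | 74.4% | 81.0 / 80.6% | 19.4% | 94.6 / 94.4% | 5.6% |
| 128 | 0.4 | 94.0% | 90.9 / 90.9% | 9.0% | 94.9 / 94.7% | 5.3% |
| 160 | 0.2 | 51.9% | 77.5 / 78.1% | 21.8% | 95.0 / 94.5% | 5.5% |
| 160 | 0.3 | 83.7% | 85.1 / 85.0% | 15.0% | 94.5 / 95.1% | 5.0% |

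With correlations 0.4 and 0.3 (3,000 trials per scenario):

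- Slopes 0.3 and 0: coverage and male error were 77% and 23% at 80 couples, 79 to 80% and 20 to 21% at 120, and 84 to 85% and 15% at 160.
- Slopes 0.3 and 0.1: coverage was 75 to 82%, and 160 couples did not help (75 to 77%).
- Equal slopes of 0.3 (120 couples): coverage was 93 to 94%.

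With no association in either gender, the chance of at least one significant finding was 6.8 to 8.7% over 64 to 160 couples and correlations from 0 to 0.5.

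**4. Where the error comes from.** Take 128 couples with slopes 0.2 and 0. Coverage for women is 94.3% in trials that split and 67.3% in trials that pool: 0.437 × 0.943 + 0.563 × 0.673 = 0.412 + 0.379 = 0.791. The pooled slope is significant in 32.3% of pooled trials, contributing 0.563 × 0.323 = 0.182 of the 0.207 male rejections, or 88%. The remaining 0.025 arises in split trials, 0.025/0.437 ≈ 6% of them. The damage is therefore done almost wholly by reading a pooled slope as the men's slope.

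**5. Checking the remedy.** A plain random-couple model assumes one residual variance. If the male/female residual SD ratio is 0.7, then ignoring correlation the women's standard error is too small by the factor √((1 + 0.49)/2) = 0.863, and the men's is too large by 0.863/0.7 = 1.23. Coverage is then P(|Z| < 1.96 × 0.863) ≈ 91% and P(|Z| < 1.96 × 1.23) ≈ 98%. Simulation with correlated partners gave 90 to 92% and 98 to 99%. Separate residual variances restore about 95%.

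**The case against.** The strongest reply is that the analysis is about the entire sample. On that reading a non-significant gender test leads to one average slope, and the interval for that average is sound: in trials that did not split it covered the average in 95.1% (slopes 0.3 and 0) and 94.5% (0.3 and 0.1). Most of the 20% are then correct rejections of no association overall, and become false only if someone writes that the association holds in men. This stands, and it limits the point to gender-specific readings. Such readings are natural, however, because the rule pools on the ground that gender does not matter.

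It can also be said that the slopes and correlations are assumed, that the large figures need a gender difference the test often misses, and that both branches are fixed in advance. All of this is true. Nor is the test always weak: with 120 couples and slopes 0.3 and 0 it splits in 72% of trials.

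Three stronger readings are tempting and lack support:

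- A reader might infer that the pooled branch omits a gender main effect. Section 4.6 lists no fixed effects and names only the clustering factor, so silence there proves nothing.
- A reader might infer that the per-gender models wrongly ignore clustering. Each couple gives one observation per gender, so each fit is valid in itself. What is lost is a joint estimate of the gender difference.
- A reader might infer that the plan promises intervals that fail. It promises none for this model; the coverage figures concern intervals that would normally accompany the slopes.

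**Conclusion.** The point holds in a limited form. The rule selects a model by a significance test and ignores the selection. If men and women truly differ by an amount the test often misses, nominal 95% intervals read as gender-specific slopes cover about 77 to 82% under most of the assumed values (75 to 85% at the extremes), and a null male slope is called significant in about 20% of trials. One interaction model keeps both close to 95% and 5% when residual variances are equal. If the slopes are equal or both zero, the rule costs little: coverage about 93%, error about 7% per slope.

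A reader might infer that the trial's main results are at risk. They are not: the association is exploratory and non-randomised, and the primary chi-square test, the between-arm t-tests and the sample size do not depend on it. The change is worth making because it is cheap, not because the trial fails without it.

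**What to change.** Replace the decision rule in section 4.6 with one model fitted whatever the interaction p-value. It should contain expected rate, gender, expected rate × gender, within-couple correlation through couple number, and separate residual variances for men and women. Report the slope for women, the slope for men and the interaction, each with a 95% CI, and optionally the average slope.

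This costs one paragraph and no new data. The downside is precision if the slopes are truly equal. With partner correlations 0.4 and 0.3 and equal variances, a gender slope has a standard error √(2/(1 + 0.4 × 0.3)) = 1.34 times that of a pooled slope. The average slope from the same model then has essentially the pooled precision, so reporting it as well recovers what is lost.

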#### 4.7 Follow-up outcomes

Whether the intervention and control group, differ in one long-term clinical (i.e. the 12-months cumulative clinical live birth rates for the observed oocyte aspiration) and three compliance outcomes, followed-up in patient's medical chart, will be analysed. The association between expected live birth rates and these long-term outcomes will also be explored on data from the entire sample.

### 5. Direct access to source data and documents

For this RCT no study-related monitoring or audits are planned. The EC review, and regulatory inspections (where appropriate) shall provide direct access to source data and other documents (i.e. patients' case sheets, etc.).

### 6. Safety reporting

#### 6.1 Definitions

##### 6.1.1 Adverse Events (AEs)

An AE is any untoward medical occurrence in a patient or clinical study subject administered a pharmaceutical product and which does not necessarily have a causal relationship with this treatment. An AE can therefore be any unfavourable and unintended sign (including an abnormal laboratory finding), symptom, or disease temporally associated with the use of a medicinal product, whether or not considered related to the medicinal product.

##### 6.1.2 Adverse Reactions (ARs)

An AR is a response to a medicinal product or experiment which is noxious and unintended. Response in this context means that a causal relationship between a medicinal product or study-related intervention and an AE is at least a reasonable possibility. ARs may arise from use of the product within or outside the terms of the marketing authorization or from occupational exposure. Conditions of use outside the marketing authorization include Special Situations.

For reporting purposes to Funder of this study, only AR related to a medicinal product of Funder must be documented by the site staff. An AR related to the intervention on the study must also be documented by the site staff, but not reported to the Funder.

##### 6.1.3 Serious Adverse Reactions (SARs)

A SAR is any AR as defined above, which also fulfils at least one of the seriousness criteria below:

- results in death;
- is life threatening (at the time of the event);
- requires hospitalization or prolongation of existing inpatients' hospitalization;
- results in persistent or significant disability or incapacity;
- is a congenital anomaly or birth defect;
- that required medical or surgical intervention to preclude of any other important medical event that did not result in any of the outcomes listed above due to medical or surgical intervention but could have been based upon appropriate medical judgement. An elective hospital admission will not be considered as a serious adverse event.

The investigator will report all SARs to the sponsor without undue delay after obtaining knowledge of the events.

##### 6.1.4 Special Situations with regards to a medicinal product of Funder

- Use of such medicinal product during pregnancy or breastfeeding: reports where embryo, fetus or child may have been exposed to medicinal products (either through maternal exposure or transmission of a medicinal product via semen following paternal exposure);
- Reports of overdose, abuse, off-label use, misuse, medication error or occupational exposure;

- Lack of therapeutic efficacy;
- Prescription error/dispensing error, e.g., due to confusion of invented names of the medicinal products;
- Drug interaction;
- Suspected transmission of an infectious agent via a medicinal product; or
- Product complaints (incl. falsified products or counterfeit products).

The investigator will report all above listed situations to the sponsor without undue delay after obtaining knowledge of the events.

#### 6.1.5 Emerging Safety Issues

Safety issues are events/observations which may occur in relation to a medicinal product of Funder and which may have major impacts on the risk-benefit balance of the product and/or patients or public health.

### 6.2 Recording of adverse events

Safety events will be recorded from informed consent signature until the day of their last embryo transfer. This study does not affect couple's treatment and we do not expect physical risks from giving patients their personalized prognosis. The personalized prognosis might, however, increase anxiety on the day of embryo transfer and this will be monitored with a validated questionnaire during the study. In addition, participant's reports of distress, potentially made to medical doctors during embryo transfer or reported on the questionnaire administered directly after the transfer will be registered.

The participant will be asked to report any adverse event related to the study-specific intervention to the study team. These reported events will be documented by the Investigator in the source documents. The following minimum information should be recorded for each AR:

- AE description of the adverse events
- Start and stop date of the AR
- Severity
- Seriousness
- Causality assessment to the study interventions
- Outcome

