### 2.3 Study parameters/endpoints

The **primary endpoint** is the proportion of women expecting directly after their fresh embryo transfer that their IVF-live delivery birth rate to be double their calculated IVF-prognosis (i.e. women's expected live birth rate  $\geq 2^* \text{prognose}$ ) In addition the proportion of men expecting their IVF-live birth rate to be double their calculated IVF-prognosis will be studied. Patient's expected IVF-live birth rates will be assessed immediately after the fresh embryo transfer with a single question coded paper-pencil questionnaire.

**Women's and men's anxiety** will be assessed with the reliable 'State-Anxiety Inventory, (STAI-state)' questionnaire disseminated in coded paper-pencil format on the day of the fresh embryo transfer (Appendix 3). The STAI-state questionnaire includes 20 questions rated on a-four-point-Likert scale and results in a score between 20 to 80 (the higher, the more anxiety).

**Patient's infertility-specific distress** will be assessed with the reliable 'Infertility Distress Scale (IDS)' questionnaire, which has been translated reciprocally to Dutch (Appendix 4). The IDS questionnaire will be disseminated via text message and online within two days of the conclusive pregnancy test after the transfers of the last (fresh or cryopreserved) embryo of the studied IVF-cycle. The IDS questionnaire includes eight questions to be rated on a-five-point-Likert scale and results in a score between 8 and 40 (the higher, the more infertility specific distress, Appendix 4).

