### **7.2 Recruitment and consent**

Couples will be asked for informed consent on the day of their oocyte aspiration. Patients who agree to participate will be asked to sign a written informed consent of which they will receive a copy.

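### Adverse-event recording under Section 6.2 closes at the last embryo transfer, before the pregnancy test and the distress questionnaire, so later non-serious events are not systematically recorded

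*Combined protocol and SAP*

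**What the plan says.** The recording window is set by the opening of Section 6.2: "Safety events will be recorded from informed consent signature until the day of their last embryo transfer". Section 7.2 fixes its start: "Couples will be asked for informed consent on the day of their oocyte aspiration". The exposure comes later. Section 2.2 states: "Intervention group: At the time of their fresh embryo transfer couples will receive a document with the following feedback", and Section 3.2 agrees.

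Section 6.2 names one foreseen harm: "The personalized prognosis might, however, increase anxiety on the day of embryo transfer and this will be monitored with a validated questionnaire during the study". It adds that distress mentioned to doctors during the transfer or "reported on the questionnaire administered directly after the transfer will be registered". It also asks participants to tell the study team of events related to the intervention. These are to be documented with a description, dates, severity, seriousness, causality and outcome.

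The IDS comes after the window. Section 2.3 schedules it "within two days of the conclusive pregnancy test after the transfers of the last (fresh or cryopreserved) embryo of the studied IVF-cycle", and Section 3.2 gives the same timing. Section 2.2 includes among its aims the "infertility specific distress experienced by patients at the time of a negative pregnancy test". Section 4.6, by contrast, dates the arm comparison of IDS scores to the day of transfer.

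**The concern.** The intervention is a piece of information, and the harm one would look for is psychological. Such harm need not show itself on the day the document is handed over. It may surface during the wait for the test or when the result arrives. The protocol treats the negative test as a moment worth measuring, and it keeps couples in the study until they have been sent the IDS. Yet the formal record of events, with severity, causality and outcome, has already closed.

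Two features make the cut-off awkward. First, for couples whose fresh transfer is also their last, it coincides with the exposure. Second, its length follows the supply of frozen embryos and not a fixed period after feedback. At stake is how complete the harms record is. The primary endpoint is not affected.

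**Working it through.** The documents give no safety figure to reproduce, so the check is a timeline. Let T be the day of the fresh transfer (feedback given) and L the day of the last transfer.

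| Event | When | Source | Inside the 6.2 window? |
|---|---|---|---|
| Consent | Oocyte aspiration | 7.2 | Yes, opens it |
| Feedback document | T | 2.2, 3.2 | Yes |
| STAI-state, both partners, both arms | T | 2.3, 3.2, 4.4 | Yes |
| Distress told to doctors or given on the questionnaire | T | 6.2 | Yes |
| Last transfer | L | 2.3 | Closes it |
| Conclusive pregnancy test | After L | 2.3 | No |
| IDS | After the test | 2.3, 3.2 | No |
| Live birth and compliance outcomes from chart | 12 to 18 months after aspiration | 2.4, 4.7 | No |
| Serious adverse reactions | When known, and yearly | 6.1.3, 6.3 | Not tied to it |

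**Recording time after exposure.** Full days recorded after feedback = L − T. Section 2.3 allows the last embryo to be fresh or cryopreserved. With no frozen embryos L = T, so L − T = 0. If a frozen transfer follows, L − T is positive, but its length is not given. The conclusive test comes after L in both cases, so it is outside the window for everyone.

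**How many couples.** The share s without frozen embryos is not in the documents. Taking the 80 per group in 3.1.2 and assuming s:

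- s = 20%: 0.20 × 80 = 16 intervention couples
- s = 40%: 0.40 × 80 = 32
- s = 60%: 0.60 × 80 = 48

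On the 64 per group that the calculation in 3.1.2 requires, the same shares give 12.8, 25.6 and 38.4, or about 13, 26 and 38.

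**Who is recorded least.** In the Appendix 7 model each additional embryo adds 0.153 to the log-odds: e^0.153 ≈ 1.17 per embryo, and e^(5 × 0.153) = e^0.765 ≈ 2.15 for five. Couples with few embryos probably have fewer to freeze. That step is an inference and not stated in the documents. If it is right, couples given lower prognoses tend to have the shorter window.

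**What the later measures can replace.** The IDS (Appendix 4) has eight rating items, scored 8 to 40 in total (2.3), with no adverse-event or free-text item. The plan compares group means and gives no rule for reviewing individual answers or linking them to the 6.2 fields. The chart review covers live birth, medical censoring, delay and discontinuation, not distress. The request in 6.2 that participants report related events has no end date of its own. It can be read as governed by the section's opening sentence, so a site could reasonably stop documenting at L.

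**The case against.** The strongest reply is that the plan observes the harm it foresees, and this largely stands. Section 6.2 foresees anxiety on the transfer day. That day is inside the window, and the STAI-state is compared by arm with a 95% confidence interval (4.4). Distress voiced at transfer is registered. Later, IDS scores (4.6) and the clinical and compliance outcomes (4.7) are compared by arm. A reader might infer from the short window that harm from the feedback goes almost unobserved. The documents do not support that.

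Nor do they support a second tempting inference, that serious distress after a failed cycle would be kept out of the yearly report. Section 6.1.3 obliges the investigator to report every serious adverse reaction once known, with no end date. Section 6.3 asks for a yearly overview of those reactions and of new safety information, again without reference to the 6.2 window. The limit is that such an event must first come to someone's attention.

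A third inference, that unequal windows bias the comparison of arms, also fails. The feedback does not change the number of embryos, so window length should balance on average under randomisation.

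It is also fair to say that distress at a negative test is not evidence of harm from feedback. Section 1 gives the opposite rationale, that unrealistically high expectations combined with repeated failure lead to distress. Such distress is expected in both arms, and a randomised IDS comparison is better suited to detecting an effect than case-by-case causality judgements.

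What the reply does not remove is the mismatch itself. Participation runs to the IDS contact, while event recording stops earlier.

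**Conclusion.** The point holds in a limited form. For couples with no frozen embryos, adverse-event recording closes on the day of feedback. For all couples it closes before the conclusive pregnancy test. What is lost is systematic documentation, with severity, causality and outcome, of non-serious or spontaneously reported intervention-related events after the last transfer. Scale-based outcomes and the reporting of known serious reactions are intact, and the primary analysis is unaffected.

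The size rests on two things. The 0 full days follow directly from the text. The number of couples (16 to 48 of 80) rests on assumed shares of 20% to 60%, which the documents neither confirm nor exclude. This is a cheap improvement to harms capture, not a flaw that undermines the trial.

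**What to change.** Amend the first sentence of 6.2 so that, in both arms, recording runs from consent through the IDS contact that follows the conclusive pregnancy test of the last transfer of the studied cycle. It should close when the IDS is completed, or at a fixed cut-off after the questionnaire is sent. The sponsor must set that cut-off, because the protocol gives a sending time but no due date. Naming the studied cycle also removes an ambiguity, since 6.2 does not say which cycle its last transfer belongs to.

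State in 6.2 that participant reports received up to that point are documented with the fields already listed there. Moving the date alone would not do this, because the IDS has no item that asks about events.

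Reconcile 4.6 with 2.3 and 3.2 on when the IDS is measured. The extended window is anchored to that contact, and the IDS is the main later measure of distress.

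Cost: a few sentences, with no new visit, since contact by text message and online is already planned. The downside is a few more reports to document, some of them distress after failed cycles that is expected in both arms and hard to attribute to the feedback.

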### 2.5 Study design

RCT (computerized randomization; 1/1 allocation sequence; no blinding)

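### Participants are asked only for adverse events they link to the intervention, and the definition rests on a drug the trial does not give, so solicited reports cannot be compared between arms

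*Combined protocol and SAP*

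**What the plan says.** Section 6.2 sets the rule for collecting events: "The participant will be asked to report any adverse event related to the study-specific intervention to the study team". The investigator documents what is reported, and the items to record include "Causality assessment to the study interventions". That list is introduced as applying to each AR, but its first item is a description of the AE.

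The definitions are in section 6.1:

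- 6.1.1: "An AE is any untoward medical occurrence in a patient or clinical study subject administered a pharmaceutical product".
- 6.1.2: "An AR is a response to a medicinal product or experiment which is noxious and unintended". The next sentence explains this as meaning that "a causal relationship between a medicinal product or study-related intervention and an AE is at least a reasonable possibility". The section also says: "An AR related to the intervention on the study must also be documented by the site staff, but not reported to the Funder".
- 6.1.3: a SAR is an AR that meets a seriousness criterion. Under 6.3 the yearly report to the Ethics Committee gives an overview of SARs and takes account of other new safety information.

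Section 6.2 describes the intervention in these words: "This study does not affect couple's treatment and we do not expect physical risks from giving patients their personalized prognosis". It names increased anxiety on transfer day as the possible harm, to be followed with a validated questionnaire. It also says that distress reported to doctors at transfer, or on the post-transfer questionnaire, will be registered. Recording runs from consent to the day of the last embryo transfer.

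Section 2.5 states that there is no blinding. Under section 2.2 controls receive a photo and the number of frozen embryos, and the intervention arm also receives the quality rating and the prognosis.

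**The concern.** Two features of the safety text work against each other and against the design.

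First, the request to participants already contains a causality judgement. A participant who does not connect an event with the intervention is not asked to report it, so the investigator's later causality assessment sees only events that passed the participant's own screen. In an open trial that screen works differently in the two arms, because only one arm has a prognosis to blame.

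Second, the AE definition is drug-trial text. Applied literally to an information sheet, it leaves the site unsure whether a bad reaction to the sheet is an AE at all. The doubt is sharpest for men, who are enrolled and assessed but need not be taking any product.

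At stake is the record of unanticipated or severe individual reactions. A reader of the final report could take an excess of reports in the intervention arm as harm when the request itself produced it, or take few reports as reassurance when events were not linked to the sheet and so never reported.

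**Working it through.** The plan gives no figure for adverse events, so the check is mainly a comparison of texts, followed by two short calculations.

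**1. Does the request treat the arms alike?** Section 6.2 limits it to events related to the study-specific intervention. By section 2.2, controls do not get the two items that make up the intervention. They may still link an event to their own sheet, the questionnaires or taking part, so their count need not be zero, but the opportunity is unequal. Section 4 plans no tabulation of events by arm.

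**2. Do the definitions agree?**

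| Section | What it hangs on | Covers a reaction to the document? |
|---|---|---|
| 6.1.1 (AE) | a pharmaceutical product | not on its wording |
| 6.1.2, first sentence (AR) | a product or an experiment | yes |
| 6.1.2, second sentence (AR) | a product or study-related intervention, linked to an AE | yes by intent, but it returns to 6.1.1 through the word AE |
| 6.2 (recording) | the study intervention, any participant | yes by intent, with AE and AR mixed |

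If the product must come from the trial, no participant qualifies, woman or man. If any product counts, whether a man qualifies depends on what he happens to receive. Neither reading fits 6.2.

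Sections 6.1.2, 6.1.4 and 6.1.5 also refer to a Funder's medicinal product, while section 10 gives funding as not applicable.

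**3. How far could the request alone separate the arms?** All inputs here are assumptions: true event rate *p*, equal in both arms; share *a* = 0.5 of events linked to the intervention and reported in the intervention arm; controls link events at a fraction *q* of that propensity, from 0 to 0.5. Reported rates are *p* × *a* against *p* × *a* × *q*. Counts use the 80 women per arm of section 3.1.2.

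| *p* | Intervention | Control, *q* = 0 to 0.5 | Per 80 women |
|---|---|---|---|
| 5% | 2.5% | 0 to 1.25% | 2 against 0 to 1 |
| 10% | 5% | 0 to 2.5% | 4 against 0 to 2 |
| 20% | 10% | 0 to 5% | 8 against 0 to 4 |

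The true difference is zero in every row. The gap closes only at *q* = 1, when controls link events as readily as the intervention arm. The table concerns solicited reports only. It does not describe spontaneous distress reports, which section 6.2 registers without an attribution condition.

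**4. What remains comparable?** Section 3.2 has men and women of both arms complete the STAI-state on transfer day. Section 4.4 compares it between arms by t-test with a 95% confidence interval, and section 4.6 does the same for the IDS. The plan's 64 women per arm for the primary outcome (50% against 25%, two-sided 5%, 80% power) is reproduced by Fisher's exact test: power is 79.4% at 63 and 80.2% at 64. With 64 per arm, a two-sided t-test at 5% has 80% power for a difference of 0.50 SD; with 80 per arm, for 0.45 SD. A moderate shift in mean anxiety can therefore be detected, whatever the participant attributes it to.

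**The case against.** The strongest reply is that the one harm the protocol expects is measured properly. Anxiety is scored in both arms and both sexes and compared with an interval, and infertility distress is compared as well. Distress reports are registered without any attribution condition. The STAI items ask directly about feeling upset, frightened, nervous and worried, so closed items do capture distress. No planned conclusion rests on event counts, the Ethics Committee report is not confined to SARs, and collecting only related events is a proportionate choice for a sheet of paper.

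Most of this stands, and it rules out three stronger readings that a reader might infer:

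- *That harm in general cannot be compared between arms.* The STAI and IDS comparisons contradict this.
- *That the control arm must show no events.* Controls can link events to other parts of the study, and their distress reports are registered in the same way.
- *That men, half the participants, are excluded.* No section says so. Section 6.2 speaks of participants, and 6.1.2 reaches beyond products. The definitions conflict; they do not state an exclusion.

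Two things survive the reply. The scales are compared as group means, so a few severe reactions may hardly move them, and no rule turns a score into a safety event. Registration of distress is passive: in the readable text the transfer-day forms have no open item (the figures in Appendix 1 are not shown), and Appendix 8 is worded for the intervention sheet.

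**Conclusion.** The point holds for solicited adverse-event reports and for the definitions behind them. The request in 6.2 is filtered by the participant's own attribution in an unblinded trial whose arms differ in what there is to attribute, so those reports cannot support a statement about one arm against the other. Sections 6.1.1, 6.1.2 and 6.2 do not agree on whether a reaction to the document, in a woman or a man, is an AE.

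The documents contain no event rate, so the size of the distortion cannot be calculated from them. On the assumed values above, reported rates differ by between 1.25 and 10 percentage points with no true difference, and the gap would vanish if controls linked events equally often.

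The primary analysis is unaffected, and average anxiety and distress can still be compared. The gap concerns unanticipated or severe individual reactions. It is a limited defect, worth correcting because the correction is cheap.

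**What to change.** - Reconcile 6.1.1, 6.1.2 and 6.2 so that the AE and AR definitions cover any participating woman or man and refer to the feedback document, and use AE and AR consistently in the recording list.
- Reconcile the wording on a Funder's medicinal product in 6.1.2, 6.1.4 and 6.1.5 with section 10.
- Put the same neutral open question to both arms on the transfer-day form, without asking what caused the event. Record every answer, and let the investigator assess causality afterwards.
- Add to section 4 a descriptive table of reports by arm and sex.
- Do not add a question to the IDS message unless the recording window is aligned with it. The IDS follows the conclusive pregnancy test, whereas recording in 6.2 ends on the day of the last embryo transfer.

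The cost is protocol wording, one open line on a form already in use and one table. The downside is that some events unrelated to the feedback will have to be recorded and assessed.
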